13.10. Scheduled Follow-up Visits

After receiving notice of completed study procedure, Medtronic will provide the target dates and windows for each visit to the center. Should a subject miss a visit or the visit fall outside the pre-specified window, a study deviation must be reported and the original follow-up schedule maintained for subsequent visits.

Data analyses include follow-up visits, regardless of whether the visit occurs within the window. Therefore, a late visit is preferred over a missed visit but must be accompanied by a deviation. Follow-up visit windows are listed in Table 8 and are based on days after the index ablation procedure.

Table 8: Follow-up Schedule

Occurrence/ Visit	Window (Calculated days after the ablation procedure)		
	Window Start	Target	Window End
Enrollment/Baseline	-30 days	-15 days	Day 0
Index Cryoablation Procedure	Day 0	Day 0	Day 0
6 week phone call	35 days	39 days	42 days
3 month office	91 days	91 days	121 days
6 month office	165 days	180 days	195 days
12 month office	365 days	365 days	395 days

The following information is required to be collected at the follow-up visits:

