13.12. Holter and TTM Management

Market-released Holvers will be distributed by a core lab to centers after activation has occurred. All subjects will wear a Holter in conjunction with their 6 and 12 month office visits. Holvers will then be sent back to the center after they have been worn by the subject. The core lab will be responsible for adjudication of atrial arrhythmias for the primary objective of the study. The core lab will manage maintenance, calibration and tracking of the Holvers.

Holter distribution logs will be provided to European centers. The logs must be maintained and updated when Holvers are received and returned to the core lab.

Market-released TTMs will be distributed by a core lab to centers after activation has occurred. All subjects will transmit weekly and symptomatic ECGs via the TTM system following their 3 month office visit. The TTM system will be sent back to the core lab at the end of the study. The core lab will be responsible for adjudication of atrial arrhythmias for the primary objective of the study. The core lab will manage maintenance, calibration and tracking of the TTMs.

TTM distribution logs will be provided to European centers. The logs must be maintained and updated when TTMs are received and returned to the core lab.

13.13. 12 lead Electrocardiograms

Market-released 12-lead ECG machines will be distributed by a core lab to centers after activation has occurred. All 12-lead ECGs starting with the one occurring at the 3 month office visit will be sent to the core lab. The 12-lead ECG machine will be sent back to the core lab at the end of the study. The core lab will be responsible for adjudication of atrial arrhythmias for the primary objective of the study. Copies of additional source documents may be requested. The core lab will manage maintenance, calibration and tracking of the 12-lead ECG machine.

12-lead ECG distribution logs will be provided to European centers. The logs must be maintained and updated when 12-lead ECG machines are received and returned to the core lab.

13.14. [REDACTED]

Follow Appendix B if the subject is enrolled in the sub-study [REDACTED]

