The probability of a subject achieving effectiveness success at 12 months (365 days) will be estimated using survival analysis, the Kaplan-Meier method. The standard error will be approximated using Greenwood's formula. A two-sided 95% log-log confidence interval for the probability will be constructed.

For every treated subject, day 0 is defined as the day of the index cryoablation procedure. For subjects with treatment failure, the survival date will be set to the date of the treatment failure. For subjects without treatment failure through 12 months, those subjects will be censored at the last study contact date

Medtronic Confidential

recorded on CRF which may include the last study visit, the exit date, or death date. If a subject without a treatment failure is lost to follow-up, the censoring date will be set to the last known study visit date.

For the component of the endpoint, documented AF/AT/AFL, if this documentation resulted from rhythm monitoring occurring at the 12-month visit within the 12-month visit window, the date of recurrence will be set to 365 days from the study ablation procedure so that these events will be counted as treatment failures in the 12-month Kaplan-Meier analysis.

Performance Requirements

If the lower bound of the 95% confidence interval at 12 months is greater than the performance goal of 40%, the objective will be considered met.

Rationale for Performance Criteria

The choice of twelve month follow-up and acceptable success rate of 40% performance criteria was selected based on the 2012 HRS/EHRA/ECAS Expert Consensus Statement on Catheter and Surgical Ablation of Atrial Fibrillation: Recommendations for Patient Selection, Procedural Techniques, Patient Management and Follow-up, Definitions, Endpoints, and Research Trial Design, provides recommendations for success rates in clinical trials. The recommendation for evaluating the efficacy of a treatment for persistent AF is as follows: *"If minimum chronic success rate is selected as an objective effectiveness endpoint for a clinical trial, we recommend that the minimum chronic acceptable success rate for persistent AF at 12-month follow-up is 40%."*¹

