6.2.2.1. Hypothesis

The following hypothesis will be tested in a one-sided test at the 0.025 significance level:

Ho: $ns \leq 40\%$

Ha: $ns > 40\%$

where ns is the probability of treatment success at 12 months.

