6.2.2.3. Analysis Methods

The probability of a subject achieving effectiveness success at 12 months (365 days) will be estimated using survival analysis, the Kaplan-Meier method. The standard error will be approximated using Greenwood's formula. A two-sided 95% log-log confidence interval for the probability will be constructed. For every treated subject, day 0 is defined as the day of the index cryoablation procedure. For subjects with treatment failure, the survival date will be set to the date of the treatment failure. For subjects without treatment failure through 12 months, those subjects will be censored at the last study contact date recorded on CRF which may include the last study visit, the exit date, or death date. If a subject without a treatment failure is lost to follow-up, the censoring date will be set to the last known study visit date.

For the component of the endpoint, documented AF/AT/AFL, if this documentation resulted from rhythm monitoring occurring at the 12-month visit within the 12-month visit window, the date of recurrence will be set to 365 days from the study ablation procedure so that these events will be counted as treatment failures in the 12-month Kaplan-Meier analysis. This objective will be analyzed in the mITT dataset: all enrolled subjects who have the Arctic Front Advance Cardiac CryoAblation Catheter inserted into vasculature will be included.

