6.2.2.4. Performance Requirements

If the lower bound of the 95% confidence interval for the primary endpoint at 12 months is greater than the performance goal of 40%, the objective will be considered met. Rationale for the choice of performance goal is included in the CIP.

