7.1. Sample Size Determination for Efficacy Endpoint

Sample size was estimated using Proc Power in SAS 9.4. The calculation was designed to find the number of analyzed subjects required for a one-sided exact binomial test ($\alpha = 0.025$) to have 90% power in declaring the event rate significantly greater than the efficacy performance goal of 40%, when in fact the true rate of treatment success at 12 months is 54%. Attrition from enrollment to 12-month follow-up was assumed to be 10%, implying $150 * (1 - 0.1) = 135$ and $\text{floor}(165 * (1 - 0.1)) = 148$ subjects analyzed at one year for the PMA-S and PMDA datasets, respectively. The sample size calculation under these conditions can be replicated with the following SAS code:

```
proc power;
  ods output=Power=Power;
  test = Binomial;
  alpha = 0.025;
  power = 0.9;
  ntotal = 135;
  ncrit = 66;
  actual = 0.54;
  alpha = 0.0224;
  power = 0.899;
  ntotal = 148;
  ncrit = 72;
  actual = 0.54;
  alpha = 0.0202;
  power = 0.917;
run;
```

	N Total	Upper Crit Val	Actual Alpha	Power
(PMA-S)	135	66	0.0224	0.899
(PMDA)	148	72	0.0202	0.917

[figure not shown]
The power calculation outlined above is based on the binomial test, which is conservative compared to the power provided by the Kaplan-Meier methods (described in 6.2.2) that will actually be used. In the case of Kaplan-Meier analysis, attrition is partial: data is included for all subjects up until they exit the study, so only subjects who exit prior to day 0 (index ablation) will provide no information to the analysis.

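### The day-365 dating rule covers only recordings made at the 12-month visit, so AF caught by TTM or an unscheduled ECG between day 366 and that visit can go uncounted while later AF found at the visit counts; the effect is small.

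*SAP*

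**What the plan says.** - **Estimate and test.** SAP 6.2.2.3 and CIP 17.3.1 estimate success by Kaplan-Meier at 12 months, defined as 365 days, with Greenwood errors and log-log limits. A failure takes the date on which it happened. SAP 6.2.2.1 states: "The following hypothesis will be tested in a one-sided test at the 0.025 significance level". SAP 6.2.2.4 adds that if the lower 95% limit "at 12 months is greater than the performance goal of 40%, the objective will be considered met".
- **The exception.** AF/AT/AFL is dated to day 365 "if this documentation resulted from rhythm monitoring occurring at the 12-month visit within the 12-month visit window". The reason given is "so that these events will be counted as treatment failures in the 12-month Kaplan-Meier analysis".
- **Visit timing.** CIP 13.10: "Follow-up visit windows are listed in Table 8 and are based on days after the index ablation procedure". In Table 8 the 12-month window opens on day 365, which is also the target, and closes on day 395.
- **Other recordings in the same days.** CIP 13.12: "All subjects will transmit weekly and symptomatic ECGs via the TTM system following their 3 month office visit". The TTM device is returned at the end of the study, not on day 365. Under CIP 13.11, 12-lead ECGs from unscheduled visits go to the core lab.
- **Which recordings define failure.** SAP 6.2.2.2 names Holter, TTM and 12-lead ECG together, with no order of precedence and no upper day limit.

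Neither document extends the day-365 dating to TTM or unscheduled ECGs made after day 365.

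**The concern.** Up to day 365 every source counts. From day 366 to the visit, only recordings made at the visit count. Two subjects with visits on day 385 show the result:

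| Subject | TTM, day 370 | Visit Holter and ECG, day 385 | Dated | 12-month result |
|---|---|---|---|---|
| 1 | AF | clear | day 370 | success |
| 2 | no AF | AF | day 365 | failure |

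The subject with the earlier documented recurrence succeeds and the one with the later recurrence fails. What separates them is which instrument caught the AF.

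A third case is not settled: AF on TTM at day 370 and again at the day-385 visit. If the visit recording triggers the rule, the subject fails at day 365. If failure is dated by first documentation, the date is day 370 and the subject succeeds. Two programmers could code this differently, and SAP section 8 requires independent programming of the primary analysis.

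At stake is the estimate compared with 40%, and whether its definition is the same for every subject.

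**Working it through.** **1. The plan's own figures.** Exact binomial, null rate 0.40, true rate 0.54 (SAP 7.1):
- n = 135, at least 66 successes: alpha 0.0224, power 0.899.
- n = 148, at least 72 successes: alpha 0.0202, power 0.917.

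Both match the SAP. Neither depends on the dating rule.

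**2. What the rule does to the estimate.** Take 150 subjects, 72 failures before day 365 and no early censoring. With S the estimate, the lower limit is S^exp(1.96·√[(1−S)/(nS)] / |ln S|). Add three subjects with a recurrence after day 365:
- All three recorded at a day-380 visit and dated to day 365: S = 75/150 = 0.500, lower limit 0.418.
- All three recorded by TTM on day 372, visit recordings clear: S = 78/150 = 0.520, lower limit 0.437.

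The earlier recordings give the better result.

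**3. Where one subject matters.** Same formula, n = 150:
- 72 successes: S = 0.480, √[0.520/72] = 0.0850, lower limit 0.398. Not met.
- 73 successes: S = 0.487, √[0.513/73] = 0.0839, lower limit 0.405. Met.

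**4. How many subjects.** The documents give no hazard after day 365, no TTM compliance and no distribution of visit days. Assumptions: 0.54 × 150 = 81 subjects free of failure near day 365; onset hazard 2–5% per 30 days; TTM compliance 60–90%; 40–80% of recurrences sustained; visits spread over days 365–379 or 365–395. Simulated ranges per 150 treated:

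| Group | Subjects |
|---|---|
| AF on TTM after day 365, visit clear (uncounted on either reading) | 0.01 to 0.39 |
| The above plus AF on both TTM and visit (uncounted under first-documentation dating) | 0.24 to 1.67 |
| AF first seen at the visit (counted as failure) | 0.29 to 1.71 |

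In points of success rate, the upper ends of the first two rows are 0.39/150 = 0.26 and 1.67/150 = 1.1.

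**5. False-pass rate.** At a true rate of 40% there are 0.40 × 150 = 60 failure-free subjects, not 81, so step 4 is rescaled by 60/81.
- Natural reading: at most 0.39 × 60/81 = 0.29 subjects, or 0.19 points.
- First-documentation reading: 0.24 to 1.67 subjects become 0.18 to 1.24, or 0.12 to 0.82 points.

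P(at least 73 of 150) is 1.93% at p = 0.400, 2.2% at 0.4019 (the rescaled maximum), 2.3% at 0.4026 (without rescaling) and 2.60% at 0.405. The natural reading stays below 2.5%. First-documentation dating could pass 2.5% towards the top of its range.

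**The case against.** The strongest defence is that the stated quantity is success at 365 days. A TTM recording on day 370 lies outside it, so leaving it out is no error. The visit rule is then a conservative exception: because the window opens on day 365, most visit recordings would otherwise be lost, and the rule only adds failures. This stands in part. Against a strict day-365 endpoint the plan omits nothing. But the plan does not hold to that cut-off: visit recordings up to day 395 count and TTM recordings in the same days do not.

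Four stronger readings are tempting, and the documents do not support them:
- **The error always favours success.** This is true only against counting every source through the visit. Against strict day-365 dating the rule adds failures.
- **The rule defeats its own purpose.** The purpose clause refers to recordings made at the 12-month visit. TTM was never within it.
- **Better TTM compliance turns failures into successes.** This needs first-documentation dating. On the natural reading a subject with AF at the visit fails whether or not the TTM was sent, and one with clear visit recordings succeeds either way. The phrase about the first clinical failure in SAP 6.2.2.2 concerns blanking-period recurrences and is not a dating tie-break.
- **The false-pass rate rises to about 3.5%.** That takes a full 1.0-point shift at a true 40%, which is outside even the rescaled first-documentation range.

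It might also be said that TTM is part of 12-month-visit monitoring. CIP 13.10.4 lists a 12-lead ECG and a 24-hour Holter for that visit; CIP 13.12 describes TTM as a separate weekly and symptom-triggered stream.

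**Conclusion.** The concern holds as an inconsistency in the dating rule with a small effect. Followed as written, the rule can put two subjects in the wrong order, and it leaves open the case of AF on both a post-365 TTM and the visit recordings.

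On the more natural reading about 0.01 to 0.4 of 150 subjects are affected, at most 0.26 points of success rate. Under first-documentation dating it is up to about 1.7 subjects, or 1.1 points. Both ranges rest entirely on the assumed hazard, compliance, persistence and visit timing; visits close to the day-365 target would leave almost no gap. The issue could change the conclusion only at the boundary between 72 and 73 successes of 150. A reader might infer that the 2.5% level is broken; on the natural reading it is not. The case for acting is that the correction is cheap and removes an ambiguity from the primary endpoint.

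**What to change.** In SAP 6.2.2.3, and in CIP 17.3.1 to match, apply one cut-off to all recordings. State that any core-lab-adjudicated AF/AT/AFL on TTM, Holter, or scheduled or unscheduled 12-lead ECG, after day 365 and up to and including the in-window 12-month visit, is dated to day 365, and that this applies also when an earlier post-365 recording exists. Add a sensitivity Kaplan-Meier estimate that uses actual dates for all recordings, and report both.

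**Cost.** One sentence and one further run, on recordings the core lab already adjudicates. SAP 6.8 allows a new SAP version. Under CIP 17.1 a CIP amendment is needed only if a principal feature changes; if the sponsor judges that it does, the approvals in CIP 19.4 apply.

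**Downside.** The reported success rate may fall slightly, by the amounts in the verdict. Subjects with later visits also have a somewhat longer period in which AF can be found, up to 30 days; the actual-date analysis shows how much that matters.

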6.2.2.4. Performance Requirements

If the lower bound of the 95% confidence interval for the primary endpoint at 12 months is greater than the performance goal of 40%, the objective will be considered met. Rationale for the choice of performance goal is included in the CIP.

6.2.2.5. Sensitivity Analyses

A sensitivity analysis will be conducted to estimate the potential impact of subjects with less than 12 months of follow-up at the final analysis, which is described in more detail in section 6.5.

In the event a subject is enrolled, treated, but later discovered they did not meet eligibility, a sensitivity analysis will be conducted to understand the impact of these subjects. The same analysis methods will be utilized as described in section 6.2.2.3, but those subjects not meeting eligibility will be excluded.

6.2.3. Primary Safety Objective

Demonstrate an acceptable safety profile of the pulmonary vein isolation (PVI) ablation procedure.

6.2.3.1. Hypothesis

The following hypothesis will be tested in a one-sided test at the 0.025 significance level:

Ho: PS \geq 13%

Ha: PS < 13%

Where PS is the probability of a safety event through 12 months.

6.2.3.2. Endpoint Definition

A primary safety event is defined as a serious procedure-related or serious system-related adverse event including the following:

- Transient ischemic attack (within 7 days of ablation procedure)
- Cerebrovascular accident (within 7 days of ablation procedure)
- Major bleeding that requires transfusion (within 7 days of ablation procedure)
- Cardiac perforation, tamponade or pericardial effusion (within 7 days of ablation procedure)
- Pulmonary vein stenosis (>75% reduction within 12-months of ablation procedure)
- Myocardial infarction (within 7 days of ablation procedure)
- Phrenic nerve injury (unresolved at 12-months)
- Atrio-esophageal fistula (within 12-months of ablation procedure)
- Death (within 7 days of ablation procedure)

6.2.3.3. Analysis Methods

The probability of a safety event at 12 months (365 days) will be estimated using survival analysis, the Kaplan-Meier method. The standard error will be approximated using Greenwood's formula. A two-sided 95% log-log confidence interval for the probability will be constructed.

For every treated subject, day 0 is defined as the day of the index cryoablation procedure. For subjects with a safety event, the survival date will be set to the date of the safety event. For subjects without a safety event, those subjects will be censored at the last study contact date recorded on CRF which may include the last study visit, the exit date, or death date. If a subject without a safety event is lost to follow-up, the censoring date will be set to the last known study visit date.

For subjects with a repeat ablation within 12 months, the start of the survival analysis will not reset. Day 0 will remain the day of the index cryoablation procedure. Safety events related to the repeat ablation procedure occurring on or prior to 365 days post the index cryoablation procedure will be counted as safety events and count against the primary safety objective. This objective will be analyzed in the mITT dataset: all enrolled subjects who have the Arctic Front Advance Cardiac CryoAblation Catheter inserted into vasculature will be included.

6.2.3.4. Performance Requirements

If the upper bound of the two-sided 95% confidence interval at 12 months is less than the performance goal of 13%, the objective will be considered met.

6.2.4. Secondary Objective

Demonstrate an improvement in quality of life between baseline and 12 months as measured by the AFEQT (Atrial Fibrillation Effect on QualiTy-of-life) and Medical Outcome Short Form-12 (SF-12) questionnaires.

The secondary objective, Quality of Life, will be evaluated to gain additional information about the performance of the Arctic Front Advance Cardiac CryoAblation catheter. There are three hypotheses

tested in the objective (separate hypothesis tests related to the AFEQT questionnaire, the physical component score of the SF-12 questionnaire, and the mental component score of the SF-12 questionnaire). A Hommel multiple testing procedure will be utilized to maintain an overall type I error rate of 0.025 for this objective². The simultaneous analysis of secondary objectives is described in more detail in section 6.5.

6.2.4.1. AFEQT

The AFEQT questionnaire will be utilized for this objective. The questionnaire is an atrial fibrillation specific health-related quality of life questionnaire to assess the impact of AF on a subject's life. The overall score ranges from 0 – 100, with 0 corresponds to complete disability and 100 corresponds to no disability.

Hypothesis

The following hypothesis will be tested in a one-sided test at the 0.025 significance level:

$$H_0: \Delta AFEQT = 0$$

$$H_a: \Delta AFEQT > 0$$

Where $\Delta AFEQT$ is the change in AFEQT score from baseline to 12 months.

Analysis Methods

Change in AFEQT score is defined as 12-month AFEQT score minus baseline AFEQT score. Change in AFEQT scores will be assessed utilizing a one-sample t-test. A two-sided 95% confidence interval will be calculated based on the t-distribution.

Additionally, summary statistics (e.g. mean, SD, median, range) and graphical methods will be used to summarize the change in AFEQT scores from baseline through 12 months. The outcome variable for this objective requires both a baseline and a follow-up assessment of AFEQT scores with answers for all questions. Analysis will be performed on the mITT dataset for those subjects that have completed at least 50% of the questions for each subscale at baseline and 12-months.

Performance criteria

If the p-value from the one-sample t-test after adjusting for the Hommel procedure is < 0.025 , the objective will be considered met.

Additional Analyses

The AFEQT questionnaire has three subscale scores, Daily Activities Subscale, Treatment Concern, and Treatment satisfaction. Each subscale ranges from 0 – 100, where 0 corresponds to low quality-of-life and 100 corresponds to high quality of life.

Change in AFEQT subscale score is defined as 12-month AFEQT subscale score minus baseline AFEQT subscale score. A two-sided 95% confidence interval will be calculated based on the t-distribution.

² Hommel, G. A stagewise rejective multiple test procedure based on a modified Bonferroni test. *Biometrika* 1988; 75, 383-386.

answered. Analysis will be performed on complete cases within the mITT dataset, in subjects that have completed both a baseline and 12-month questionnaire.

Performance criteria

If the p-value from the one-sample t-test after adjusting for the Hommel procedure is < 0.025 , the objective will be considered met.

Additional Analyses

As with AFEQT assessments, SF-12 scores will be assessed as 6-month visits in addition to baseline and 12-month visits. While only the baseline and 12-month assessment will be used in the hypothesis tests for one-year change in SF-12 physical and mental health scores, all graphical and descriptive presentations of SF-12 outcomes will show data from all three timepoints. Additionally, results from a repeated measures analysis using all available data may be shown in the final report, to provide information on the degree of change in QoL in the first and second half years after the cryoablation procedure. The following code for SAS proc mixed provides a template for this analysis:

```
proc mixed data=...;
  class ...;
  model ...;
  ods output ...;
run;
```

```
proc mixed data=...;
  class ...;
  model ...;
  ods output ...;
run;
```

